10.3. Tertiary efficacy analyses

- 1) Speed of onset of benefit will be analysed in three ways. Firstly, the difference in the mean change in disease severity (SASSAD) at 4 weeks compared to baseline will be analysed using a t-test. Secondly, the final 4 week period (weeks 12 to 16) will be examined for the delayed treatment group using a single sample t-test. Finally daily bother scores from the daily symptom diaries for the first 4 weeks of the trial will be plotted for both groups.
- 2) Likely carry over effect will be examined graphically using the daily bother scores during the 16 week trial period for the immediate installation group. This information will be useful in planning the design of future trials in this area.
- 3) A responder will be defined as a 20% or 50% decrease in SASSAD score. Two logistic regression models will be used to investigate predictors of response as listed in section 6.2.

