| Water Engineer Home screening visit Home visit to assess suitability of residence for installation of softener Estimate salt requirements and assess availability of storage for salt supply Test water hardness | Research Nurse Recruitment Visit clinic appointment Baseline characteristics Eligibility criteria checked SASSAD POEM Utility measures (DFI and EQ-5D) Weigh medications UTP questionnaire Digital photo of index site Saliva sample Explanation and issue of Diary 1 Explanation of accelerometer (Actiwatch TM) Issue Water Softener Information sheet Randomisation | Water Engineer At 0–2 weeks ♦ Install unit (Group A) within 10 working days of DAY ZERO (date of recruitment visit) ♦ Advice given to reduce soap consumption etc. ♦ Issue water sampling containers + prepaid envelopes | Research Nurse Clinic appointment At 4–6 weeks ◇ SASSAD ◇ POEM ◇ Digital photo of index site ◇ Saliva sample (if not obtained at baseline) ◇ Collection of week 1 Actiwatch™ data ◇ Weigh medications ◇ Collection of Diary 1 and Issue of new Diary 2 | Trial Manager At 8 to 9 weeks | Research Nurse Clinic appointment At 12–14 weeks SASSAD POEM Utility measures Digital photo of index site Weigh medications Collection of Week 11-12 Actiwatch™ data and Actiwatch™ Collection of Diaries 2 Issue Diary 3 Explanation of cross-over phase | Water Engineer At 12–14 weeks ◇ Remove unit (Group A) within 10 working days of 12 week anniversary of installation ◇ Install unit (Group B) within 10 working days of 12 week appointment with RN; retest water hardness. ◇ Advice given to reduce soap consumption etc (Group B) ◇ Issue water sampling containers and pre-paid envelopes (Group B) | Research Nurse Water Engineer At 16 to 18 weeks Clinic appointment with Research Nurse to carry out: SASSAD POEM Utility measure Collection of Diary 3 Visit by Water Engineer to: Remove unit (Group B), if they do not wish to purchase unit, within 10 working days of 4 week anniversary of installation Reinstall unit (Group A) if they wish to purchase unit at first convenient time after 16 week appointment with RN. |

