10.5 Tertiary analyses

- ♦ Changes in SASSAD at 4 weeks will be assessed using Student's t-test.
- ♦ For the within group analyses, mean change in disease severity (SASSAD) at week 4 (relative to baseline) compared to mean change in disease severity at week 16 (relative to week 12) will be analysed using a paired samples t-test. These analyses will be used to explore speed of onset and possible carry-over effects.

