1. INTRODUCTION

This analysis plan details the planned statistical analyses for the Softened Water Eczema Trial (SWET).

This is a single-blind, parallel group, randomised controlled trial of 12-week duration, followed by a 4-week cross-over period. The objective is to assess whether the installation of an ion-exchange water softener improves eczema in children, and if so to establish the likely cost and cost-effectiveness of the intervention.

Participants are randomised to one of two groups on a 1:1 basis. The first group have a water softener installed the first 12 weeks of the trial followed by a 4 week washout period. The second group, the delayed treatment group, have the water softener installed for four weeks from week 12 onwards.

| | STUDY PERIOD = 16 weeks | |
|---------|--|----------------|
| | 0 to 12 weeks | 12 to 16 weeks |
| Group A | Usual eczema care + water softener installed (n = 155) | Unit removed |
| Group B | Usual eczema care + delayed installation (n = 155) | Unit installed |

Throughout this document Group A will be referred to as the immediate installation group, and Group B as the delayed treatment group.

The analyses described in this document will be performed by the designated statistician at the MRC Clinical Trials Unit. All data will be analysed using Stata Version 10.1.

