3.3. Tertiary Endpoints

If a beneficial effect is found the following tertiary analyses will be performed.

- 1) Speed of onset of benefit will be analysed in three ways. Firstly, the difference in the mean change in disease severity (SASSAD) at 4 weeks compared to baseline. Secondly, the final 4 week period (weeks 12 to 16) will be examined for the delayed treatment group. Finally the daily bother scores will be examined for the first 4 weeks of the trial for both groups.
- 2) Likely carry over effect will be examined using the full 16 week trial period for the immediate installation group. This information will be useful in planning the design of future trials in this area.
- 3) Predictors of response model, including baseline factors (see section 6.2)

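### The delayed-group onset test in SAP 10.3 is uncontrolled: a single-sample t-test over weeks 12 to 16 cannot separate softener benefit from drift, and exposure at the final visit is not fixed at four weeks

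*Combined protocol and SAP*

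**What the plan says.** SAP 3.3 and 10.3 list three analyses of speed of onset. The first is a between-group t-test of SASSAD change from baseline to week 4. The second says that weeks 12 to 16 "will be examined for the delayed treatment group using a single sample t-test". The third is a plot of daily bother scores over the first four weeks. For the second, the SAP states neither the outcome variable nor the null value. All three are conditional: "If a beneficial effect is found the following tertiary analyses will be performed".

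Protocol 10.5 handles the same question differently. Within each group, the mean SASSAD change from baseline to week 4 is "compared to mean change in disease severity at week 16 (relative to week 12) will be analysed using a paired samples t-test". The SAP does not carry this contrast over and does not say why.

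On exposure, SAP section 1 says that the delayed group will "have the water softener installed for four weeks from week 12 onwards". Table 1 of the protocol says: "Install unit (Group B) within 10 working days of 12 week appointment with RN". The 12-week visit has its own window ("Clinic appointment At 12–14 weeks SASSAD"). The last nurse visit is set at 16 to 18 weeks. Removal of Group B's unit is timed from the four-week anniversary of installation; the nurse visit is not.

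**The concern.** A single-sample test against zero has no change as its null hypothesis. Anything that moves SASSAD between the two visits enters the estimate: natural course, season, changes in usual treatment, and changes in behaviour by families who know that the unit has just been fitted. The nurse's blinding protects the scoring but not these sources. A small p-value could then be reported as onset within four weeks when part or all of the change is drift. Drift towards worsening would do the opposite and hide a real onset.

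Speed of onset also needs a clock that starts at installation. The SAP treats weeks 12 to 16 as the exposure period, but the schedule lets installation come later and has no rule for counting actual days of softened water. A null result could reflect short exposure rather than slow onset.

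**Working it through.** **Number of children.** The SAP's sample-size inputs are a 4-point difference (20% of a baseline of 20), SD 10, 5% two-sided (sidedness assumed for this calculation) and 90% power.

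- Per arm: n = 2 × (1.960 + 1.282)² × 10² / 4² = 131.3, so 132.
- Total: 264. With 15% attrition, 264 / 0.85 = 310.6. This agrees with the stated 310.

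So about 132 Group B children are expected to have data.

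**Rejection under drift alone.** Suppose the softener has no effect within four weeks of being fitted, and the mean improves by d points for other reasons. The test statistic then follows a non-central t distribution with 131 degrees of freedom and non-centrality d / (SD/√132). The two-sided 5% critical value is 1.978.

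- SD 10 (the SAP's sample-size value, borrowed here): standard error 10/√132 = 0.870. An observed mean fall of 1.978 × 0.870 = 1.7 points is significant.
- SD 7 (assumption): standard error 7/√132 = 0.609. A fall of 1.978 × 0.609 = 1.2 points is significant.

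| Assumed drift (points) | p<0.05, SD 10 | p<0.05, SD 7 |
|---|---|---|
| 0 | 5% | 5% |
| 1 | 21% | 37% |
| 2 | 63% | 90% |
| 3 | 93% | over 99% |

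For drifts of 1 point or more, almost all of these rejections are in the direction of benefit. Both 1.7 and 1.2 points are less than half of the 4-point difference that the trial treats as clinically relevant. The probabilities are not conditioned on the gate in SAP 3.3.

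**The protocol's paired contrast.** This compares Group B's change over weeks 12 to 16 with its own change over weeks 0 to 4, when it had no unit. If drift is equal in both periods it cancels: in simulation with 131 children, SD 10 and drift of 1 or 2 points, the error rate in the direction of benefit was 2.5% to 2.6%. If drift differs between the periods, it does not cancel. Entry requires a SASSAD of at least 10, so regression to the mean would tend to enlarge the improvement over weeks 0 to 4 and bias the contrast against the softener.

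**Exposure at the final visit.** Exposure is the week of the final visit minus the week of installation. With installation in weeks 12 to 14 and the final visit in weeks 16 to 18:

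- shortest: 16 − 14 = 2 weeks
- as SAP section 1 assumes: 16 − 12 = 4 weeks (also 18 − 14 = 4)
- longest: 18 − 12 = 6 weeks

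The same arithmetic applies to Group A at the week-4 visit. Installation at 0 to 2 weeks and a visit at 4 to 6 weeks give 4 − 2 = 2 to 6 − 0 = 6 weeks.

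**The case against.** The strongest reply is that little rests on this test. It is tertiary, it runs only if a benefit is found, and the first onset analysis listed is a randomised comparison at week 4 that drift common to both arms cannot bias. Protocol section 3 calls the final four weeks exploratory. All of this stands. A reader might infer from the table above that the plan risks declaring an ineffective softener beneficial; the documents do not support that, because the primary inference comes from the randomised 12-week comparison. The gate does not cure the narrower fault, however. It addresses whether there is benefit by week 12, not whether benefit begins within four weeks.

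Second, the drift sizes are assumed. The documents give none, nor an SD for weeks 12 to 16. Enrolment over 18 to 20 months spreads season across children, and new treatments are discouraged. This stands too: the figures show how sensitive the test is, not how much drift to expect.

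Third, the SAP names no outcome or null value, and a paired t-test is itself a single-sample test on differences. The SAP may have meant the protocol's contrast. That is possible, but its text mentions only weeks 12 to 16, so the two sections need reconciling either way.

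Fourth, a reader might infer that some children could have no exposure at all by the final visit. Taking every window literally, 16 − (14 + 2) = 0. That needs a late 12-week visit, the full installation lag and an early final visit only two weeks later. The engineer column of Table 1 is headed 12 to 14 weeks, which on a plain reading rules it out. The 16-to-18-week window may even have been meant to absorb the lag, though nothing requires it.

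**Conclusion.** The concern holds as a limited point about one of three gated, tertiary onset analyses. As written, the single-sample test cannot attribute Group B's change over weeks 12 to 16 to the softener, and the SAP has lost the reference period that the protocol supplied. With 132 children and SD 10, assumed drift of 1 to 3 points gives a significant result in about 21% to 93% of trials without any onset within four weeks. This rests on reading the test as SASSAD change against zero, on borrowing the sample-size SD, and on drift values that are illustrative only. Exposure at the final visit is about 2 to 6 weeks rather than a fixed four, provided installation falls in weeks 12 to 14. Neither the primary analysis nor the conclusion about benefit at 12 weeks is affected.

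**What to change.** In SAP 10.3 item 1:

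- Replace the single-sample test with Group B's mean SASSAD change over weeks 12 to 16 and its confidence interval, presented by actual days since installation and labelled as uncontrolled.
- State that the onset conclusion rests on the randomised week-4 comparison already listed first. Report it with actual days since installation in Group A, because the same lag applies there.
- Reconcile this item with protocol 10.5. If the paired contrast is kept, state that it removes only drift that is equal in both periods and may be distorted by regression to the mean after the entry threshold.
- Reconcile the four weeks of exposure in SAP section 1 with the windows in Table 1.

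A between-arm comparison of week-16 SASSAD adjusted for week 12 is a tempting substitute but should not serve as the onset test. Group A's unit comes out after week 12, so the contrast mixes onset in B with loss in A. It also conditions on a post-randomisation score that differs between the arms once a benefit has been found. If A is d points lower at week 12, keeps that benefit, and B has no onset, the adjusted contrast has expectation −d(1 − b), where b is the within-arm slope. With d = 4 and b = 0.7 (assumption), that is a spurious difference of 4 × 0.3 = 1.2 points.

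The cost is SAP wording and no new visits or assessments, given that installation dates are recorded. The downside is that the within-group result has no p-value.

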5.5 Starting and stopping treatment

Units will be installed in the participants' homes as soon as possible after being randomized to treatment (ideally within 10 working days).

If participants choose to withdraw from the study, any units that have been installed will be removed as soon as is practicably possible. Participants will be asked to complete an end of study questionnaire at this time and diaries will be collected.

If participants are away from the main residence for any reason, this information will be recorded in their treatment diaries. Absence from the home will be included in a predictors of response model and will be used as a measure of treatment adherence for the (secondary) per protocol analysis.

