10. STATISTICS

10.1 Statistical design

Analyses have been planned in order to place emphasis on objective outcomes that are less likely to be influenced by the potential bias inherent in a single-blind study. Nevertheless, a variety of additional tools are to be used that reflect more closely the disease process throughout the study period. Some of these are relatively objective indicators of disease activity (such as nocturnal movement and treatment application), whilst others reflect subjective concepts (such as self-reported symptoms in the POEM), in order to capture the many health-related dimensions affected by eczema.

The planned analyses should answer the following questions:

- 1. Does exposure to softened water for 12 weeks improve the symptoms and severity of eczema, compared to standard care?
- 2. Does softened water improve quality of life for patients and their carers?
- 3. Are water softeners a cost-effective treatment for children with atopic eczema?

In addition, tertiary analyses will explore the following parameters:

4. How quickly the benefits of softened water become evident.

5. How quickly the benefits of softened water are lost once treatment is stopped.

The main intention-to-treat analysis will be conducted at 12 weeks. An additional per protocol analysis will also be conducted for the primary outcome in order to test the proof of concept.

A sub-group analysis will also be conducted based on the presence or absence of mutations on the gene filaggrin (*see* section 12). Mutations on the filaggrin gene have been associated with dry skin and may therefore be a useful predictor of treatment response.

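### The 4-week daily bother plot counts from recruitment, not installation, so Group A's apparent onset is shifted later by about the installation delay (minor; cheap to supplement)

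*Combined protocol and SAP*

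**What the plan says.** Protocol 10.1 lists among its exploratory questions: "How quickly the benefits of softened water become evident". SAP 10.3 item 1 answers it in three ways: a t-test of SASSAD change from baseline to week 4, a single-sample test of weeks 12 to 16 in the delayed group, and a diary plot: "Finally daily bother scores from the daily symptom diaries for the first 4 weeks of the trial will be plotted for both groups". SAP 3.3 describes the plot as follows: "Finally the daily bother scores will be examined for the first 4 weeks of the trial for both groups".

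Protocol Table 1 (under 9.4) defines the origin of the schedule. The baseline column is Day ZERO, the recruitment visit. Baseline SASSAD is taken then, and the list of tasks includes "Explanation and issue of Diary 1". The next column, headed 0 to 2 weeks, reads "Install unit (Group A) within 10 working days of DAY ZERO (date of recruitment visit". Protocol 5.5 is looser: "Units will be installed in the participants' homes as soon as possible after being randomized to treatment (ideally within 10 working days". Protocol 9.5 has the same qualifier.

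Table 1 allows the 4-week visit at 4 to 6 weeks. Diary 1 is collected and Diary 2 issued at that visit, and Diary 2 is collected at the 12-week visit. Installation is used as a time origin for removing units (Table 1) and in the per-protocol exposure rule (SAP 5). Neither SAP 3.3 nor SAP 10.3 mentions installation date or days of exposure. SAP 3.3 makes all these analyses conditional on a beneficial effect.

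**The concern.** Speed of onset means time from first exposure to softened water. On the plan's axis, day 0 is the recruitment visit, and exposure in Group A begins on a different later day for each child. The early part of the Group A curve therefore averages children who have softened water with children who do not yet have it. A real response would look later than it is, and a sharp one would also look more gradual. The diary plot is the only onset analysis of Group A with daily resolution, so a reader would look there for an answer in days.

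**Working it through.** **Inputs from the documents**
- Day ZERO is the recruitment visit; Group A installation is due within 10 working days, column headed 0 to 2 weeks (protocol Table 1).
- The target is not a hard limit (protocol 5.5 and 9.5).
- Plot window: 28 days of trial time (SAP 3.3 and 10.3).
- 4-week visit: day 28 to day 42 (Table 1).

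**Inputs assumed.** The distribution of installation delay and the shape of the response are not in the documents. The curves below are illustrations.

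**1. The plan's own window.** Ten working days from any weekday, with no public holidays, is 14 calendar days. This agrees with 0 to 2 weeks.

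**2. Share of the plotted window before softening** = installation day / 28.

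| Installation day | Share before softening |
|---|---|
| 0 | 0/28 = 0% |
| 7 | 7/28 = 25% |
| 14 | 14/28 = 50% |
| 21 (target missed) | 21/28 = 75% |

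Half is thus the maximum only if the target is met. With delays uniform on 0 to 14 days the average share is 25%.

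**3. Gradual response.** Let the effect after u days of exposure, as a fraction of its plateau, be f(u) = 1 − 2^(−u/7), with the delay uniform on 0 to 14 days. Averaging over the delay gives the apparent effect A(t) on trial day t:
- for t ≤ 14: A(t) = (1/14) × [t − (7/ln 2) × (1 − 2^(−t/7))]
- for t ≥ 14: A(t) = 1 − 0.541 × 2^(−(t−14)/7), where 0.541 = (1/14) × (7/ln 2) × 0.75

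Results:
- A(14) = 1 − 0.541 = 0.459, and A(28) = 1 − 0.541 × 0.25 = 0.865.
- A(t) = 0.5 at t = 14 + 7 × log2(0.541/0.5) = 14.8, against 7 days of exposure.
- The shift is 14.8 − 7 = 7.8 days. Of this, 7 days is the mean delay and 0.8 comes from curve shape.
- The 10% to 90% rise takes 22.2 days on the exposure axis and 25.2 days on the trial axis.
- At the mean exposure on trial day 14 (7 days) the true value is 0.50 against 0.459. At the mean exposure on day 28 (21 days) it is 1 − 2^(−3) = 0.875 against 0.865.

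For a response this gradual, nearly all the distortion is an offset and little is smearing.

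**4. Sharp response.** Take a full effect appearing 3 days after installation, with the same uniform delay. The 50% point moves from day 3 to day 3 + 7 = 10. The 10% to 90% rise goes from 0 to 0.8 × 14 = 11.2 days. Here the smearing is substantial.

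**5. Week-4 SASSAD.** For a visit on day 28, the mean effect relative to 28 days of exposure depends on how long benefit takes to build:
- linear build over 14 days: 100%, even if every unit goes in on day 14
- linear build over 28 days: 75% with uniform delay, 50% if every unit goes in on day 14

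If the visit is held 28 days after installation (day 42 for a day-14 installation, inside the allowed window), exposure is 28 days and nothing is lost.

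**The case against.** The SAP does not define when trial weeks begin, and its introduction describes Group A as having the softener throughout the opening 12 weeks, as though trial time and installed time coincided. That wording does not remove the problem. The only stated origin is Day ZERO in Table 1, the diary starts there, and no re-timing rule is given.

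Several stronger readings are tempting, and the documents do not support them:
- **Exposure at the 4-week SASSAD varies threefold, from 2 to 6 weeks.** That pairs the latest installation with the earliest visit, and the earliest installation with the latest visit. The two windows have the same width and may move together in practice. No section says that visits follow installation, but none says that they are independent of it.
- **All the onset analyses start at recruitment.** The delayed-group analysis covers weeks 12 to 16. It has its own lag, since Group B's unit is due within 10 working days of the 12-week visit, but not this origin.
- **The length of future trials would be misjudged.** The plan's remark about planning future trials concerns carry-over, not onset.

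The present axis also has a real merit. A common origin preserves the randomised comparison, whereas installation delay arises after randomisation and Group B has no installation before week 12. That argument stands, and it is a reason to add a display without replacing the planned one. SAP 10.3 item 2 also plots Group A's bother scores over all 16 weeks, so a response after day 28 would still be seen.

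**Conclusion.** The point holds for the Group A diary plot, as a minor one. With the installation target met, 0 to 14 of the 28 plotted days precede softening. Apparent onset moves later by about the installation delay, plus smearing that is slight for a gradual response and marked for a sharp one. The direction follows from the documents. The size does not, because they give no delay distribution: the move from day 7 to about day 15 rests on an assumed uniform delay and a 7-day half-time, and 7 of its 7.8 days are the assumed mean delay.

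The week-4 SASSAD t-test is affected only if visits are not scheduled from installation and benefit takes more than about 2 weeks to develop. A reader might infer that the main result is at risk. It is not: these analyses are tertiary and conditional on benefit, and the point does not bear on the primary analysis or the sample size.

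**What to change.** In SAP 10.3 item 1, and to match in 3.3:
1. Keep the plot in trial time, state that its origin is Day ZERO, and keep the week-4 randomised t-test.
2. Add a Group A plot of daily bother by days since installation, to day +28, with the number of children contributing on each day. A child installed on day 14 needs diary data to day 42, which Diaries 1 and 2 cover.
3. For reference, show Group B from a notional matched date, Day ZERO plus the median Group A delay, labelled as descriptive.
4. Report the distribution of recruitment-to-installation times, and the actual days since installation at the 4-week SASSAD.

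The cost is a few lines of SAP text and one merge of installation dates. These dates should already be held, since unit removal and the per-protocol exposure rule both need them. No visit or data item changes. The downside is that Group B's origin is notional, so the added plot is not a strictly randomised comparison and should sit beside the planned one.

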8.3 Randomisation and blinding

Participants will be entered into a web-based randomisation programme by the Trial Manager, or Research Nurse. This will randomise them to one of the 2 treatment arms based on a computer generated code, using random permuted blocks of randomly varying size. This will be created by the Nottingham Clinical Trials Support Unit (CTSU) in accordance with their standard operating procedure, and held on a secure server. The randomisation will be stratified by age, disease severity (baseline SASSAD \leq 20, or SASSAD score \geq 20) and recruiting centre. Access to the sequence will be confined to the CTSU Data Manager. Allocation to treatment arms will be in the ratio 1:1 and the Trial Manager will access the treatment allocation for each participant by means of a remote,

internet-based randomisation system developed and maintained by the Nottingham CTSU. The allocation group will be indicated to the Trial Manager only after baseline data have been irrevocably entered into the randomisation programme. The sequence of treatment allocations will be concealed until interventions have all been assigned and recruitment and data collection are complete.

The research nurses will be blinded to treatment allocation throughout the study period and the trial statistician will analyse the results based on treatment code, using an analysis plan finalised prior to revealing the coded allocation sequence. Only after the analysis is complete will the actual treatment arms corresponding to treatment codes be revealed. The only study personnel in direct contact with study participants will be the research nurses and water engineers. The trial manager and study support staff at the co-ordinating centre in Nottingham will have telephone contact with parents of participants. Trial participants will continue to see healthcare professionals for their usual eczema care.

Since participants will not be blinded to the study intervention, an objective primary outcome has been chosen in order to minimise response bias, The primary outcome of disease severity, measured using the Six Area Six Signs Atopic Dermatitis scale (SASSAD) will be assessed by the research nurses who are blind to treatment allocation. This scale is based purely on physical examination of the skin and does not require input from the participants themselves. Other secondary objective outcomes include nocturnal movement (measured using accelerometers) and the use of topical therapy.

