8.3. Derived Variables

SASSAD scores will be computed prior to data entry. This will be checked using the individual components within the analysis files.

The proportion of time spent moving during the night will be obtained using accelerometers. The average of the first three nights of usable data at week 0 and the last three nights of usable data at week 12 will be used. Usable data is defined as values greater than 5% and less than 95% of the night spent moving to remove outliers. If there are less than three usable nights data, then this variable will be considered missing.

Patient Orientated Eczema Measure (POEM) scores will be calculated as a score between 0 and 28 based on seven symptoms. Parents are asked to state the number of days in the last week their child has been affected by each symptom. These are scored as follows; no days=0, 1-2 days=1, 3-4 days=2, 5-6 days=3 and everyday=4. The POEM score is the calculated as the sum of these 7 individual scores.

Totally Controlled Weeks (TCW) will be defined as zero days with an eczema bother score greater than 4 and zero days where "stepping up" of treatment was needed. Well-Controlled Weeks (WCW) will be defined as two days or less with an eczema bother score greater than 4 and two days or less days where "stepping up" of treatment was needed. The eczema score is recorded by the parent each day using a symptom diary and is based on how much bother the child's eczema has been that day. The score is on a scale from 0 to 10 where 0 equals no bother at all and 10 equals the most bother you can imagine. The definition of "stepping up" varies from child to child and is documented in the symptom diary for the parent to refer to after discussion with the nurse at the beginning of the trial.

Dermatitis Family Impact (DFI) scores will be calculated as a score between 0 and 30 based on ten questions. Parents are asked to state how much the child's skin problem has affected the family over the last week. These are scored as follows; not at all=0, a little=1, a lot=2 and very much=3. The DFI score is the calculated as the sum of these 10 individual scores.

Age (in years and months) will be calculated at randomisation.

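### The SAP examines loss of benefit after unit removal in Group A only by plotting unblinded parents' bother scores, and drops the SASSAD analysis of Protocol 10.5 without explanation

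*Combined protocol and SAP*

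**What the plan says.** The question is a stated one. Protocol 10.1 lists among its tertiary parameters: "How quickly the benefits of softened water are lost once treatment is stopped". Protocol section 3 gives the same purpose for the last four weeks in the active group and calls those analyses exploratory.

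Protocol 10.5 sets out a SASSAD analysis within each group. The change from baseline to week 4 is compared by paired t-test with the "mean change in disease severity at week 16 (relative to week 12"), to explore both speed of onset and carry-over.

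The SAP differs:

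- SAP 3.3(2) names no measure: "Likely carry over effect will be examined using the full 16 week trial period for the immediate installation group".
- SAP 10.3(2) names one, and a method, for Group A over the 16 weeks: "Likely carry over effect will be examined graphically using the daily bother scores".
- SAP 3.3 makes the whole set conditional: "If a beneficial effect is found the following tertiary analyses will be performed".

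On who scores what, SAP 8.3 says of bother: "The eczema score is recorded by the parent each day using a symptom diary". Protocol 8.3 says that families are not blinded and that for this reason "an objective primary outcome has been chosen in order to minimise response bias". That outcome is SASSAD, scored by research nurses who are to be blinded throughout the study period. Protocol 9.1.1 and Table 1 schedule a nurse visit with SASSAD at week 16 for both groups.

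**The concern.** In Group A the family bypasses the unit itself on returning home from the 12-week visit (Protocol 9.5), and an engineer then removes it. A rise in reported bother after that date coincides with a withdrawal that the parent knows about. It could reflect a loss of benefit, an expectation of one, or both, and a plot cannot tell these apart. Protocol 8.3 chose SASSAD to limit this kind of bias.

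The SAP applies the same reasoning elsewhere. Its footnote to 3.2 explains that the Likert improvement item was left off the case report forms partly because it was too exposed to bias in a single-blind trial, and prefers improvement measured by SASSAD. SAP 10.3(2) moves in the opposite direction and does not say why.

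At stake is the quality of the answer to one exploratory question, which the SAP says will help in designing later trials. As the SAP stands, that answer would have no number attached and would rest on an unblinded score, while a blinded score from the same children goes unused.

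**Working it through.** **1. The two documents side by side, for Group A in weeks 12 to 16.**

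| | Protocol 10.5 | SAP 10.3(2) |
|---|---|---|
| Measure | SASSAD | Daily bother, 0 to 10 |
| Scored by | Nurse, to be blinded | Parent, not blinded |
| Method | Paired t-test of two 4-week changes | Plot |
| Estimate or interval | Available from the test | None |
| Reason for the change | – | None given |

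No SAP analysis names Group A's week-16 SASSAD. For the delayed group, SAP 10.3(1) keeps a single-sample t-test over weeks 12 to 16, without naming the outcome in that sentence.

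**2. Reproducing the plan's sample size.** Inputs from Protocol 10.2 and SAP 4: baseline SASSAD 20, difference 20% (so 4 points), SD of change 10, power 90%, significance 5% (taken as two-sided), attrition 15%.

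n per arm = 2 × [10 × (1.960 + 1.282) / 4]² = 131.3. The total is 2 × 131.3 / 0.85 = 309, or 311 if n is first rounded up to 132. The stated 310 reproduces and is not in dispute.

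**3. Precision of the SASSAD change from week 12 to week 16 in Group A.** Evaluable children: 155 × 0.85 = about 131. Half-width of the 95% interval = t(0.975; 130) × SD / √131 = 1.978 × SD / 11.45.

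The documents give no SD for a 4-week change after removal. The 10 is carried over from the sample-size section, so a range is shown.

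| Assumed SD | Half-width (points) | Power for a 4-point change |
|---|---|---|
| 6 | 1.04 | >99% |
| 8 | 1.38 | >99% |
| 10 | 1.73 | >99% |
| 12 | 2.07 | 97% |

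At SD 10, power is 62% for a 2-point change and 93% for a 3-point change. The 4 points are the plan's between-group difference at week 12. They serve here only as a yardstick, because the plan sets no target for loss of benefit.

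**4. The Protocol 10.5 contrast.** This is a difference between two changes, so its SD is 10 × √[2(1 − r)], where r is the correlation between the changes and each has SD 10. The documents do not give r. For r from −0.5 to +0.5 the half-width runs from 2.99 down to 1.73, and is 2.44 at r = 0. The contrast asks whether the last four weeks differ from the first four. The change from week 12 to week 16 measures the loss itself more directly.

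**The case against.** The best defence of the SAP is that the question asks how quickly benefit is lost. A single SASSAD taken at the 16-week visit (Table 1 allows weeks 16 to 18) gives the size of any loss at that visit and nothing about its speed. The diary is the daily record of severity after removal. This stands: the two measures answer different parts of the question, and the plot should not be removed or treated as worthless.

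A second defence is that a within-group change has no concurrent untreated control, so a narrow interval around it does not make it a clean estimate of carry-over. Natural fluctuation and season remain in it. This also stands, and the estimate must be labelled accordingly. The same limitation applies to the bother plot, which is also within one group and is unblinded as well.

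Two stronger readings are tempting, and the documents support neither:

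- A reader might infer that no blinded analysis of loss of benefit was ever planned. That is true of the SAP but not of the documents together. Protocol 10.5 plans one, and neither document says that it is withdrawn.
- A reader might infer that the arms should be compared on week-16 SASSAD to supply the missing control. Group B receives its unit in those same weeks (Protocol 3 and 9.5; SAP 1). Such a contrast would mix loss in Group A with onset in Group B, and a difference could arise wholly from Group B improving.

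**Conclusion.** The point holds as an unexplained discrepancy between protocol and SAP, with a cheap remedy. For Group A the SAP replaces a planned analysis of a blinded score with a plot of an unblinded one, and gives no estimate. Lack of precision does not justify the omission. The SASSAD change would be known to about ±1.7 points, given 15% attrition and an SD of 10 for the 4-week change, and to about ±1.0 to ±2.1 for SDs from 6 to 12. Its value also depends on the nurses staying blinded to week 16, as the protocol intends.

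The point is minor. The period is exploratory, and the analysis is tertiary and conditional on a benefit being found. SAP 5 rests primary inference on the 12-week endpoint alone. A reader might infer that the trial's main conclusion is exposed to parental expectation through this analysis. It is not.

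**What to change.** In SAP 10.3(2), add Group A's mean SASSAD change from week 12 to week 16 with a 95% confidence interval. Describe it as an uncontrolled within-group estimate of the size of any loss of benefit. Keep the daily bother plot and give its purpose as showing timing. Name the measures in SAP 3.3(2) so that the two sections agree.

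Reconcile this with Protocol 10.5 by either retaining its paired comparison or stating why the simpler change replaces it. Do not add a comparison of the arms at week 16 as a measure of carry-over.

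The cost is a few lines of SAP text and one summary of data already scheduled for collection. The downside is one more exploratory estimate, which cannot separate loss of benefit from natural fluctuation or season.
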